6.0 ADVERSE EVENT REPORTING

6.1 Adverse Events

Definition: any unfavorable medical occurrence in a human subject including any abnormal sign, symptom, or disease.

Attribution (relatedness), Expectedness, and Seriousness: the definitions for the terms listed that should be used are those provided by the Department of Health and Human Services' Office for Human Research Protections (OHRP). A copy of this guidance can be found on OHRP's website:<http://www.hhs.gov/ohrp/policy/advevtguid.html>

The surgeon will discuss the expected risks of the surgery with the participant and participant and a separate surgical consent for the surgery acknowledging the risks. Expected risks of the surgery are listed below.

- **Perioperative complications:**
iatrogenic injury, convert from laparoscopic approach to open procedure, use of other

hemostatic devices or therapies, blood transfusion

- **Postoperative complications:**

Secondary bleeding/hematoma, delirium, failure to thrive, urinary retention, surgical site infection, urinary tract infection, C-diff, colitis, ileus, delayed gastric emptying, fistula, anemia, pneumonia, intraabdominal abscess, atrial dysrhythmia, myocardial infarction, cellulitis, deep vein thrombosis/pulmonary embolism, anastomotic leakage, re-intervention (operational), blood transfusion, sepsis, death.

The above are complications of the surgical procedure and may be experienced by all patients on whom a Whipple procedure is performed. Surgical complications are routinely identified and documented during the data abstraction process for the American College of Surgeons National Surgical Quality Improvement Program® (NSQIP). NSQIP has very detailed and specific definitions used to assess these postoperative morbidities. For the purposes of this study, the NSQIP definitions for the surgical complications will be utilized.

Surgical complications will not be considered adverse events associated with the study, unless unanticipated and possibly related to the use of the Thunderbeat device. If an adverse event is reported, details related to the event will be obtained from medical record review and direct communication with the PI for severity and relatedness assessment. The adverse event will then be recorded as part of the research and reported as necessary. If it is determined by the PI that the event is anticipated from surgery and not related to the device, it will not be reported as an adverse event as part of this study.

6.2 Unanticipated Problems

Definition:

- unexpected (in terms of nature, severity, or frequency) given (a) the research procedures that are described in the protocol-related documents, such as the IRB-approved research protocol and informed consent document; and (b) the characteristics of the subject population being studied;
- related or possibly related to participation in the research (possibly related means there is a reasonable possibility that the incident, experience, or outcome may have been caused by the procedures involved in the research); and
- suggests that the research places subjects or others at a greater risk of harm (including physical, psychological, economic, or social harm) than was previously known or recognized.

Potential perioperative complications that could occur due to the use of the Thunderbeat device include but are not limited to:

- **Thunderbeat Device**:**

Cracking, breaking, or deformation of the components of the Thunderbeat™ probe tip or jaw, or the detaching of the fragment from the Thunderbeat probe tip or jaw during or after the surgical procedure, and burning of unintended tissue. Probe damage detected during surgery will trigger audible and visual generator alarms.

***Please note that these risks may not occur during surgery and that they are the same risks as using any other similar device for the same indication that is currently on the market.*

6.3 Noncompliance

Definition: failure to follow any applicable regulation or institutional policies that govern human subject's research or failure to follow the determinations of the IRB. Noncompliance may occur due to lack of knowledge or due to deliberate choice to ignore regulations, institutional policies, or determinations of the IRB.

6.4 Serious Noncompliance

Definition: noncompliance that materially increases risks that result in substantial harm to subjects or others, or that materially compromises the rights or welfare of participants.

6.5 Protocol Exceptions

Definition: A planned deviation from the approved protocol that is under the research team's control. Exceptions apply only to a single participant or a singular situation.

Pre-approval of all protocol exceptions must be obtained prior to the event.

6.6 Reporting to the Human Research Protection Office (HRPO) at Washington University:

The PI is required to promptly notify the IRB and Olympus, the study sponsor, of the following events:

- Any unanticipated problems involving risks to participants or others which occur at WU, any BJH or SLCH institution, or that impacts participants or the conduct of the study.
- Noncompliance with federal regulations or the requirements or determinations of HRPO.
- Receipt of new information that may impact the willingness of participants to participate or continue participation in the research study.

These events must be reported to HRPO within **10 working days** of the occurrence of the event or notification to the PI of the event. The death of a research participant that qualifies as a reportable event should be reported within **1 working day** of the occurrence of the event or notification to the PI of the event.

6.7 Time frame for Reporting Required Events

Reportable adverse events that are determined to be unanticipated and related to the Thunderbeat device will be recorded and reported for 90 days following the Whipple procedure. Events considered to be possibly, probably, or definitely related to standard of care therapy will not be reported.

Deaths	
Any reportable death while on study or within 90 days of study	Immediately, within 24 hours, to PI and the IRB
Adverse Events/Unanticipated Problems	

Any reportable adverse events that are related and unanticipated problems as described above in Section 6.2 (other than death)	Immediately, within 24 hours, to PI and within 10 working days to the IRB
All adverse events that are related and unanticipated problems regardless of grade and attribution should be submitted cumulatively	Include in DSM report
Noncompliance and Serious Noncompliance	
All noncompliance and serious noncompliance as described in Sections 6.3 and 6.4	Immediately, within 24 hours, to PI and within 10 working days to the IRB

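### Sections 6.1, 6.2, 6.7, 7 and 8 disagree on whether a device-related event that is anticipated, or possibly due to standard care, is recorded and reported

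*Combined protocol and SAP*

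**What the plan says.** **Section 6.1** lists the expected risks of the operation, opening the perioperative list with "iatrogenic injury, convert from laparoscopic approach to open procedure". It then states: "Surgical complications will not be considered adverse events associated with the study, unless unanticipated and possibly related to the use of the Thunderbeat device". Its closing sentence uses a different test. If the investigator judges an event "anticipated from surgery and not related to the device, it will not be reported as an adverse event as part of this study".

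**Section 6.2**, headed Unanticipated Problems, defines these as unexpected in light of the protocol, at least possibly related to the research, and suggesting more risk than was already recognized. Under the same heading it lists complications the device may cause: damage to the probe tip or jaw, detached fragments, "and burning of unintended tissue". A note says that similar marketed devices carry the same risks.

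**Section 6.7** first provides for recording and reporting, over 90 days, of events that are both unanticipated and device-related. Its second sentence is: "Events considered to be possibly, probably, or definitely related to standard of care therapy will not be reported". Its table makes unanticipated problems as described in 6.2 reportable. For the DSM report it asks that related events and unanticipated problems "regardless of grade and attribution should be submitted cumulatively".

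**Section 7** calls for the adverse event form only when an event is both unanticipated and related. **Section 8** sends research-related adverse events to the institutional review office and the sponsor, and does not ask whether they were anticipated.

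**The concern.** The study team needs one answer to a simple question: when the device may have contributed to an event, is a form completed? Two filters make that answer uncertain.

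The first is the requirement that the event be unanticipated, which appears in some places and not in others. The second is the standard-of-care exclusion in 6.7, which applies even when the link to standard care is only possible. The device is used during an operation that every participant would have anyway, so a burn or a bleed can nearly always be called possibly related to standard care.

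Under 6.1 the investigator assesses relatedness, and under 5.2 the surgeon cannot be blinded. Whichever sentence prevails will therefore be chosen case by case, with the allocation known. At stake is whether the device-attributed safety record is complete enough for the monitoring committee and for the adverse event incidences promised in 9.4.

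**Working it through.** The plan gives no figure to reproduce, so the check compares the rules as logical conditions.

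**Inputs**

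- A (6.1, the rule on surgical complications): a complication counts only if unanticipated and possibly device-related.
- B (6.1, closing sentence): omits only what is anticipated and not device-related.
- C (6.7, first sentence): provides for events that are unanticipated and device-related.
- D (6.7, second sentence): excludes anything even possibly related to standard care.
- E (Section 7): form triggered by an unanticipated, related event.
- F (Section 8): research-related adverse events are reported, with no condition on anticipation.

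**Step 1. Apply the rules to device-related events.** Related is taken to include possibly related. C and E do not expressly exclude anticipated events; they leave them out by not providing for them.

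| Device-related event | Points away from recording or reporting | Points towards it, or does not exclude it |
|---|---|---|
| 1. Unanticipated; standard care not a possible cause | none | A, B, C, E, F |
| 2. Unanticipated; standard care a possible cause | D | A, B, C, E, F |
| 3. Anticipated; standard care not a possible cause | A (if a surgical complication); C and E by omission | B, F |
| 4. Anticipated; standard care a possible cause | A (if a surgical complication); C and E by omission; D | B, F |

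Only class 1 gets a consistent answer. Three of the four classes do not. This counts classes, not expected events.

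**Step 2. Place the 6.2 device list.** By the section heading, probe breakage and burns are unanticipated and fall in class 1 or 2. By the definition beneath that heading, harms which the protocol names and describes as shared with similar devices could be anticipated, which puts them in class 3 or 4. A burn could also be read as the iatrogenic injury on the expected-risk list in 6.1.

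**Step 3. See what is captured by another route.** Section 9.1 makes iatrogenic injury, secondary bleeding, transfusion, abscess, leakage and re-intervention secondary endpoints, with no attribution filter. Appendix B collects complications from the day of surgery to 90 days. A bleed, or a burn that injures, is therefore counted in either arm, although no endpoint or visit item asks whether the device was responsible.

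A broken tip without injury is different. Neither 9.1 nor Appendix B names device malfunction. Because 6.1 defines an adverse event as a medical occurrence in a person, such a malfunction may not reach Section 8 either. Its capture then rests on reading the 6.2 list as unanticipated, and on D not being applied.

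**Step 4. Identify the outputs affected.** These are the adverse event form (Section 7), the cumulative DSM submission (6.7), and, if drawn from that form, the toxicity summary (Section 8) and the procedure-related adverse event incidence (9.4). Sample size and alpha are not touched.

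**The case against.** A coherent reading can be defended. The expected risks in 6.1 are those of the surgery, and the device risks are set apart in 6.2 under a heading that calls them unanticipated. The 6.7 table then makes 6.2 problems reportable, and 6.6 sends unanticipated problems to the IRB and the sponsor. The 6.1 rule on surgical complications does not clearly reach a cracked probe tip, which is a malfunction. The DSM row is also not a request for all events, since its subject is already limited to related events and unanticipated problems. It is poorly worded, but weak evidence of a contradiction. Finally, a randomized comparison of unfiltered complications is better safety evidence than attributed event forms.

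Most of this stands. A reader might infer that the plan simply discards burns and broken tips and would leave the device with a misleadingly clean record. The documents do not support that: the 6.2 heading and the 6.7 table point towards reporting, and clinical harms are compared by arm as endpoints.

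The objection does not dispose of three things. The second sentence of 6.7 still has no exception for an event that may be due to both device and standard care, and it sits directly above a table confined to reportable events. The 6.2 definition still conflicts with its own list. A malfunction without injury still has no endpoint to fall back on.

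**Conclusion.** The point holds as an internal inconsistency, not as a rule that removes known device harms. Three of four classes of device-related event receive conflicting instructions. Followed literally, 6.7 would keep mixed-attribution device events out of reporting. If the 6.2 harms are classed as anticipated, malfunctions without injury could also miss the adverse event form and the DSM report.

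The number of events affected cannot be estimated, because the documents give no rate for device events. With 30 patients in the device group, one omitted event moves an incidence by 1/30 = 3.3 percentage points. That is a property of the group size and does not predict under-reporting.

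The conclusion assumes that standard of care therapy in 6.7 includes the operation itself, which the section does not define, and that device-attributed summaries would be built from the Section 7 form. It should be corrected, because it bears on safety monitoring and is cheap to put right.

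**What to change.** Reconcile 6.1, 6.2, 6.7, 7 and 8 into one recording rule:

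1. Limit the standard-of-care exclusion in 6.7 to events judged not related to the device, in line with the closing sentence of 6.1.
2. Trigger the Section 7 form for any possibly device-related event and any device malfunction, whether or not anticipated, with grade and attribution, and include these in the DSM report.
3. State whether the device complications listed in 6.2 are classed as anticipated or unanticipated.
4. Align the 6.1 rule on surgical complications, the first sentence of 6.7 and Section 8 with this rule.
5. Keep expedited IRB reporting for unanticipated problems, so that broader recording does not become broader expedited reporting.

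The cost is a wording amendment and a few more forms in a 60-patient trial. Endpoints, sample size and clinical care are unchanged.

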8.0 DATA AND SAFETY MONITORING

In compliance with the Washington University Institutional Data and Safety Monitoring Plan, the Principal Investigator will provide a Data and Safety Monitoring (DSM) report to the Washington University Quality Assurance and Safety Monitoring Committee (QASMC) and to Olympus, the study sponsor, semi-annually beginning six months after accrual has opened (if at least five patients have been enrolled) or one year after accrual has opened (if fewer than five patients have been enrolled at the six-month mark).

The Principal Investigator will review all patient data at least monthly and provide an annual report to the Quality Assurance and Safety Monitoring (QASM) Committee. This report will include:

- HRPO protocol number, protocol title, Principal Investigator name, data coordinator name, regulatory coordinator name, and statistician

- Date of initial HRPO approval, date of most recent consent HRPO approval/revision, date of HRPO expiration, date of most recent QA audit, study status, and phase of study
- History of study including summary of substantive amendments; summary of accrual suspensions including start/stop dates and reason; and summary of protocol exceptions, error, or breach of confidentiality including start/stop dates and reason
- Study-wide target accrual and study-wide actual accrual
- Protocol activation date
- Average rate of accrual observed in year 1, year 2, and subsequent years
- Expected accrual end date
- Objectives of protocol with supporting data and list the number of participants who have met each objective
- Measures of efficacy
- Early stopping rules with supporting data and list the number of participants who have met the early stopping rules
- Summary of toxicities
- Abstract submissions/publications
- Summary of any recent literature that may affect the safety or ethics of the study

The study principal investigator and Research Patient Coordinator will monitor for serious adverse events on an ongoing basis. Once the principal investigator or Research Patient Coordinator becomes aware of a research related adverse event, the AE will be reported to the HRPO according to institutional guidelines and to Olympus, the study sponsor.

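### The plan does not ensure that the monitoring committee would see an excess of bleeding, fistula or leak in the Thunderbeat arm during accrual

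*Combined protocol and SAP*

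**What the plan says.** Section 6.1 lists the expected risks of a Whipple procedure. The postoperative part opens with "Secondary bleeding/hematoma, delirium, failure to thrive, urinary retention, surgical site infection" and goes on to fistula, intraabdominal abscess, anastomotic leakage, re-intervention, transfusion and death. On these events it says: "Surgical complications will not be considered adverse events associated with the study, unless unanticipated and possibly related to the use of the Thunderbeat device". The PI decides: "If it is determined by the PI that the event is anticipated from surgery and not related to the device, it will not be reported".

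Section 6.7 adds a second filter: "Events considered to be possibly, probably, or definitely related to standard of care therapy will not be reported". The row of its table that goes into the DSM report reads: "All adverse events that are related and unanticipated problems regardless of grade and attribution should be submitted cumulatively". Section 7.0 has the adverse event form completed only for unanticipated, related events.

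Section 6.2 defines an unanticipated problem as, among other things, "unexpected (in terms of nature, severity, or frequency) given (a) the research procedures", so an unusual frequency is a ground in its own right.

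Section 8.0 has the PI send a DSM report to the committee (QASMC) and to the sponsor every six months. A second paragraph has the PI look at all patient data at least monthly and report to the committee annually. The content list follows that second sentence. It includes the objectives with supporting data, efficacy measures, early stopping rules and "Summary of toxicities". Appendix B records complications in all patients at surgery, discharge, 30 days and 90 days.

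**The concern.** A poor seal or unintended heat injury could show itself after surgery as bleeding, a fistula, a leak, an abscess, a re-operation or a transfusion. All of these are on the expected list. One such event after a Whipple procedure looks ordinary, and a reviewer who sees it alone can reasonably call it anticipated and due to the operation. An excess shows only when events are counted and the arms compared.

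The trial is randomized and already records these events in both arms, so a valid comparator exists. The reporting rules do not send it to the committee. If the device raised one of these rates, the first comparison the plan clearly requires is the final analysis in 9.4, after all 30 Thunderbeat patients have been treated.

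**Working it through.** **Reading the sections together**

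1. *Entry to the adverse-event stream.* Under 6.1 a listed complication enters only if unanticipated and possibly related to the device. Under 6.7 it drops out if even possibly related to standard care. A postoperative bleed can be both, and the text does not say which rule prevails.
2. *Comparator.* Relatedness in 6.1 and in the opening of 6.7 means relation to the Thunderbeat device. A complication in a patient treated conventionally cannot meet that. The definition in 6.2 is wider (relation to taking part in the research), but an ordinary control-arm complication would not be unexpected under it.
3. *Frequency.* Section 6.2 allows it as a ground. No section gives an expected rate, a count by arm, or a step at which frequency is judged.
4. *The DSM row.* It asks for related events and, in the same sentence, sets attribution aside. Both cannot hold.
5. *Section 8.0.* The objectives item could bring in morbidity, which is an objective in 2.1 and 9.1, but it mentions neither arm nor type of complication. Toxicities are not defined and need not include events that 6.1 says are not adverse events. Stopping rules are to be reported, but none is stated anywhere. It is unclear whether the content list governs the semi-annual report, the annual report or both.

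**What a by-arm table could show**

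The plan gives no complication rate, so there is no figure of its own to reproduce. The rates below are assumptions.

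Accrual (9.3): 60 patients in 18 to 24 months.
- Per month: 60/24 = 2.5 to 60/18 = 3.33.
- At 6 months: 15 to 20 patients, or 7.5 to 10 per arm. This exceeds the five patients that 8.0 requires for a six-month report.
- At 12 months: 30 to 40 patients, or 15 to 20 per arm.

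Let T ~ Binomial(n, p1) be the number of Thunderbeat patients with the complication and C ~ Binomial(n, p0) the number of control patients. The chance of an excess of at least 3 is

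P(T − C ≥ 3) = Σ over all a, b with a − b ≥ 3 of P(T = a) × P(C = b).

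| n per arm | Stage | 10% vs 30%: expected events | 10% vs 30% | 10% both | 5% vs 20% | 5% both |
|---|---|---|---|---|---|---|
| 8 | 6 months, slow accrual (7.5 rounded up) | 0.8 vs 2.4 | 0.276 | 0.018 | 0.151 | 0.004 |
| 10 | 6 months, fast accrual | 1 vs 3 | 0.383 | 0.030 | 0.234 | 0.007 |
| 15 | 12 months, slow accrual | 1.5 vs 4.5 | 0.592 | 0.061 | 0.432 | 0.019 |
| 20 | 12 months, fast accrual | 2 vs 6 | 0.730 | 0.090 | 0.589 | 0.034 |
| 30 | Full accrual | 3 vs 9 | 0.880 | 0.137 | 0.789 | 0.065 |

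The last row comes too late to protect anyone and is given only for scale. These figures count every enrolled patient as fully followed. Complications accrue to 90 days, so a real report would hold somewhat less information.

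For 10% vs 30%, a two-sided Fisher test at 0.05 has power of about 0.15 at 15 per arm and 0.37 at 30 per arm.

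By contrast, at 15 per arm and 10% vs 30%, the adverse-event row could show none of the 1.5 + 4.5 = 6 expected events if each were classed as anticipated and not device-related. That is the lower limit of what the rules allow, not an estimate.

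**The case against.** A reader might infer that the DSM report holds nothing except the filtered events, and that an excess could not be noticed before the final analysis. The documents do not support that. The 6.7 row is one input. Section 8.0 also asks for data on the objectives, and postoperative morbidity is one. The PI looks at all patient data at least monthly and nothing bars the PI from judging frequency. Nor does the trial lack a group comparison, since 9.4 specifies one. Only an interim comparison by arm is not required.

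Two further points are fair. Section 8.0 relies on an institutional monitoring plan that is not among the documents and may ask for more. This is also a 60-patient feasibility study of a cleared device, in which few events will accrue by any report. With more than 20 listed complications, some will show a chance excess; at equal 20% rates an excess of 3 has probability 0.125 at 15 per arm.

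What stands is that a clear excess might be seen. What does not follow is that the committee is assured of seeing it. The monthly review is done by the person who makes the relatedness calls, is not described as by arm, and does not by itself inform the committee. The items in 8.0 can be met in full without a by-arm count. The small event numbers limit what the table can prove, but they do not justify leaving it out.

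**Conclusion.** The point holds as a gap in assurance. The adverse-event stream is filtered event by event on device relatedness and anticipation, it has no control arm, and no other required content supplies complications by arm. The frequency ground in 6.2 is therefore written but has no data behind it.

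The gain from closing the gap is modest at the first report and grows as data accumulate. For 10% vs 30% the chance of a visible excess is 0.28 to 0.38 at 6 months and 0.59 to 0.73 at 12 months, against 0.02 to 0.09 with equal 10% rates. For 5% vs 20% it is 0.15 to 0.23 and 0.43 to 0.59. These figures rest on assumed threefold and fourfold harms, an arbitrary threshold of 3 events, even accrual and complete follow-up. Smaller harms would often be missed. The textual finding depends on none of these assumptions.

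**What to change.** In 6.7 and 8.0, require each semi-annual DSM report to the QASMC to contain a cumulative table, by randomized arm and with the number of patients at risk, of the complications named in 6.1 and 9.1, intraoperative injuries and deaths, whatever the relatedness call. State that the frequency ground in 6.2 is judged from this table, and that it informs judgement without a formal test. Keep the PI's single-event review for expedited reporting.

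Also reconcile:
- the wording on relatedness and attribution in the DSM row of 6.7;
- the device-related rule in 6.1 with the standard-care exclusion in 6.7, for events that could be both;
- the semi-annual and annual reports in 8.0, saying which one the content list governs and what toxicities means.

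The cost is one table from data already collected at surgery, discharge, 30 days and 90 days. The drawback is real: these complications are secondary endpoints, and morbidity is part of the primary objective in 2.1, so the committee would see interim outcome counts by arm. Because the PI writes the DSM report and it also goes to the sponsor, the by-arm version should be prepared by the study statistician or data coordinator and sent to the committee only. Blood loss need not appear in it.
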